6.3.7 Concomitant Medications and Non-drug Therapies

Concomitant medications are defined as any medications take on or after the day of first dose of study treatment and on or before the day of last does of study treatment in the given dataset. This includes medications started prior to the first dose of study treatment in the given dataset and continued while on study or started after the first dose of study treatment. A windowing rule of +180 days may be applied to these subjects who have completed the study without lymphocyte follow-up. The WHO drug dictionary will be used for coding concomitant medications.

Concomitant medications will be summarized using the Study 109MS303 ITT Population and Study 109MS303 data only. The number and percent of subjects taking concomitant medications will be summarized. The most frequently taken concomitant medications, defined as those taken by at least 10% of subjects in any treatment group, will also be presented.

Additionally, summaries of first alternative MS medication used may be performed using the following analysis populations, treatment groupings, and datasets:

- Study 109MS303 ITT Population and Combined Data; and
- Study 109MS303 ITT Population and Study 109MS303 data only.

The number and percent of subjects in Study 109MS303 who previously took alternative MS medications in Studies 109MS301 or 109MS302 will also be summarized.

6.3.8 Day Ranges for Analyses by Visit

Subjects do not always strictly adhere to the visit schedule timing in protocols. Therefore, the designation of visits (or timepoints) will generally be based on the day of evaluation relative to date of first dose of study medication within a given dataset (i.e., with the date of first dose of study medication being Study Day 1), rather than the nominal visit recorded in the clinical database.

Mutually exclusive visit windows will generally be utilized to assign visits for analysis that correspond to post-baseline visits specified in the protocols. In general, for data that are summarized by visit, visits for analysis will be assigned by using a windowing scheme as described below.

Within a given dataset, the upper bound of the baseline visit window is Day 1, and the lower bound of the first post-baseline visit window is Day 2. For all other lower and upper bounds of visits, windows will end at the midpoint between scheduled visit timepoints, with the midpoint in the latter visit window.

If more than one observation occurs within the same window, data closest to the target day for the scheduled visit will be used for analysis. If more than one observation is the same distance from the target day, the last observation will be used for analysis.

However, for MRI analyses, visit windowing will only be applied when the nominal visit designation is premature withdrawal, with the lower bound of the first post-baseline visit window being Day 169 and with all other lower and upper visit bounds defined as above.

Otherwise, MRI analyses will not utilize visit windowing and will present results by nominal visit designations.

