2.2 Overall Study Duration and Follow-Up

Eligible subjects were enrolled at Week 96 (Visit 24) of their previous BG00012 study (109MS301 or 109MS302), which would serve as the Baseline Visit for this extension study. If the Baseline Visit could not be combined with Visit 24 of their previous BG00012 study, the subjects may have been randomized within 6 months of Visit 24, provided that they still were eligible for enrollment. The Baseline visit assessments may have been repeated if there was a gap in study treatment.

Subjects reported to the study site every 4 weeks for the first 24 weeks (Visit 1 through Visit 6) and every 12 weeks thereafter for up to 8 years.

Subjects who completed the Week 384 visit (Visit 36), regardless of further need to monitor lymphocytes on study, completed an End of Study Visit at Week 388 ± 7 days. For subjects who have completed Visit 36, an End of Study Visit was completed 4 weeks after their next visit (scheduled or unscheduled), regardless of further need to monitor lymphocytes on study. Subjects who permanently discontinued BG00012 prior to Week 384, regardless of further need to monitor lymphocytes on study, completed a Premature Study Treatment Withdrawal Visit within 4 weeks after their last dose of BG00012. Subjects who completed BG00012 treatment or permanently discontinued BG00012 for any reason and who had a lymphocyte count <LLN were not withdrawn from the study. These subjects were followed according to Protocol Section 11.3.

For subjects who have already completed Visit 36 (or beyond) prior to the Protocol Version 8, an End of Study Visit was completed 4 weeks after their next visit (scheduled or unscheduled), regardless of further need to monitor lymphocytes on study. For subjects who have not completed Visit 36 prior to Protocol Version 8, Visit 36 served as the last scheduled Visit and an End of Study Visit was completed 4 weeks after their next visit (scheduled or unscheduled), regardless of further need to monitor lymphocytes on study.

Premature Study Withdrawal Visits and Unscheduled Relapse Assessment Visits were performed as necessary. All efforts were made to keep the subjects' visit schedule relative to their Baseline Visit (Day 1). All subjects who discontinued the study treatment were considered to be prematurely withdrawn from the study.

The end of study is defined as the Last Patient, Last Visit for final collection of data for the primary outcome

2.3 **MRI**

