6.2.3 Datasets

The analysis populations and treatment groupings described above in Sections 6.2.1 and 6.2.2, respectively, will be utilized in conjunction with the following three datasets as appropriate:

- Combined Data, defined as data from Studies 109MS301, 109MS302, and 109MS303; and
- Study 109MS303 data only, defined as data from Study 109MS303.

Analyses utilizing Combined Treatment Grouping may include either Combined Data or Study 109MS303 data only. Analyses utilizing Study 109MS303 Treatment Grouping will include Study 109MS303 data only.

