6.4.6 Analysis Quality of life Assessments (SF-36 and EQ-5D) and Visual Function Test

The quality of life (SF-36 and EQ-5D) and Visual Function Test assessments will be summarized using the Study 109MS303 ITT Population with Combined Treatment Grouping and Combined Data. For these analyses, data following first use of alternative MS medications will be excluded.

SF-36

Scores for SF-36 will be calculated based on the standard scoring method described in the SF-36 Health Survey Manual and Interpretation Guide. This method indicates that for an individual domain where 50% or more of the item's questions are non-missing, the average of the non-missing items for that patient in that domain will be calculated, and this average is then used to impute the missing item questions response and calculate the domain score. The mental and physical component summary measures (MCS and PCS, respectively) are then calculated from the imputed domains scores.

Actual scores and change from Previous Study Baseline over time will be descriptively summarized by treatment group for the individual domains and MCS and PCS measures.

EQ-5D

The Euroqol (EQ)-5D is a generic health-related quality of life instrument which has been extensively validated. There are two components to the EQ-5D, a Health State Profile that results in calculation of an EQ-5D index score and a Visual Analog Scale (VAS) that results in calculation of the subject assessment of health scale.

For the Health State Profile, patients record their level of current health for five domains comprising a health profile: mobility, self-care, usual activities, pain/discomfort, and anxiety/depression. Scores of 1, 2, or 3 are possible responses for each of the five questions in the Health State Profile (1=no problems, 2=some problems, 3=severe problems). The digits for the five dimensions are combined in a 5-digit number describing a person's health state. A scoring formula developed by the EuroQol Group is then used to assign utility values for each patient's Health State Profile. A summary index score (EQ-5D index score) is derived from the 5 questions by conversion with this scoring formula and a table of scores.

For the VAS, patients are asked to rate their current health on a 20 cm scale from 0 to 100 where 0 represents "worst imaginable health state" and 100 represents "best imaginable health state" resulting in the subject assessment of health scale.

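### Combined Data visit windows count from the parent-study first dose, so a permitted gap before 109MS303 can put extension assessments in a later visit's window

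*SAP*

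**What the plan says.** **Time origin.** SAP 6.3.8 generally sets visits "based on the day of evaluation relative to date of first dose of study medication within a given dataset" and not by the nominal visit. SAP 6.2.3 gives "Combined Data, defined as data from Studies 109MS301, 109MS302, and 109MS303", so in that dataset the origin is the parent-study first dose. Windows end at the midpoint between scheduled visits, and the midpoint itself belongs to the later window. They are meant to match the post-baseline visits in the protocols. The only pre-dose protection is that, within a dataset, "the upper bound of the baseline visit window is Day 1".

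**Extension schedule.** SAP 2.2 has subjects attend "every 4 weeks for the first 24 weeks (Visit 1 through Visit 6) and every 12 weeks thereafter", counted from the extension Baseline Visit. That visit is normally parent Week 96. Where the two could not be combined, "the subjects may have been randomized within 6 months of Visit 24". The same section adds: "The Baseline visit assessments may have been repeated if there was a gap in study treatment".

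**Where the windows are used.** Under SAP 6.4.6 the SF-36, EQ-5D and visual function assessments "will be summarized using the Study 109MS303 ITT Population with Combined Treatment Grouping and Combined Data", and the table in 6.4.2.1 presents them by study visit. A note under Table 6.2.4.1 says lymphocyte analyses may also use Combined Data. MRI is reported by nominal visit, except premature-withdrawal scans, which are windowed with a first post-baseline bound of Day 169.

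**The concern.** The window targets and the actual visits are counted from different origins. A gap between parent Week 96 and extension Day 1 makes every extension assessment late against its Combined Data target by the length of that gap. Once the gap reaches half the spacing to the next scheduled visit, the assessment is reported under that next visit.

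Nothing in the SAP re-anchors extension visits within Combined Data. Nothing keeps a value taken before the first extension dose out of an extension post-baseline window either, because the Day 1 protection refers to parent Day 1. For a subject who had placebo or glatiramer acetate in the parent study, a repeated baseline taken before study BG00012 began could therefore appear in a column read as on-BG00012 follow-up. The error runs one way: labels can only be too late.

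**Working it through.** **The plan's own figure.** With target day = 7 × week + 1, extension Week 48 is Day 7 × 48 + 1 = 337. The midpoint of Day 1 and Day 337 is (1 + 337)/2 = 169, which is the MRI bound in SAP 6.3.8. Counting from parent Day 1 with a first scan at Week 24 (Day 169), the midpoint would be (1 + 169)/2 = 85. So Day 169 fits a midpoint rule anchored on extension Day 1, although the primary MRI analyses use Combined Data. It is not proof, since Day 169 is also the parent Week 24 target day.

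**Inputs.** Midpoint rule and origin from SAP 6.3.8. Gap of 0 to 6 months from SAP 2.2, taken here as about 182 days (26 weeks). Visit weeks from SAP 3.1 to 3.3 and 3.5, cut at Week 384.

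**Rule.** Let g be the gap in weeks. Extension Week w occurs at combined Week 96 + g + w, but its target is 96 + w. If the next scheduled week is w′, the assessment leaves its own window when w + g ≥ (w + w′)/2, that is, when g ≥ (w′ − w)/2.

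| Summary | Assessments | Spacing to next (weeks) | Gap that moves them |
|---|---|---|---|
| Visual function | Repeated baseline; Week 24 | 24 | 24/2 = 12 weeks |
| Visual function | Weeks 48 to 132 (8 visits) | 12 | 12/2 = 6 weeks |
| Visual function | Weeks 144 to 360 (10 visits) | 24 | 24/2 = 12 weeks |
| SF-36, EQ-5D | Repeated baseline; Weeks 48 to 336 (7 visits) | 48 | 48/2 = 24 weeks |
| Lymphocytes, if on Combined Data | Repeated baseline; Weeks 12 to 372 (31 visits) | 12 | 12/2 = 6 weeks |

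**Counts.**
- Visual function has 20 post-baseline visits to Week 384. A gap of 6 to under 12 weeks moves 8. A gap of 12 weeks or more moves 1 + 8 + 10 = 19, every visit before Week 384.
- SF-36 and EQ-5D: none of 8 visits move below 24 weeks; 7 of 8 move from 24 weeks.
- 12-weekly lymphocytes: 31 of 32 move from 6 weeks.
- Gaps under 6 weeks move none of these on-schedule visits.

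**Example, g = 26 weeks.**
- Visual function: the repeated baseline falls at combined Week 96 + 26 = 122. The extension Week 24 window runs from (96 + 120)/2 = 108 to (120 + 144)/2 = 132, so the repeat lands there and is the only value in it. The true Week 24 visit is at 96 + 26 + 24 = 146. The Week 48 window runs from 132 to (144 + 156)/2 = 150, so this visit is labelled Week 48. The true Week 48 visit is at 170, inside the Week 72 window (162 to 174).
- SF-36 and EQ-5D: the Week 48 window runs from (96 + 144)/2 = 120 to (144 + 192)/2 = 168. The repeat at 122 is labelled Week 48, and the true Week 48 visit at 170 is labelled Week 96.

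**A real value can also be lost.** With g = 8 weeks, visual function at true Weeks 132 and 144 falls at extension-scale Weeks 140 and 152. Both are in the Week 144 window (138 to 156). The closest-to-target rule keeps the first (4 weeks off) and drops the true Week 144 value (8 weeks off).

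**With separate origins.** If extension day is counted from the first extension dose, g drops out. Misassigned on-schedule visits are then 0 of 20, 0 of 8 and 0 of 32, and a repeated baseline falls at or before Day 1.

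**The case against.** The best defence is that the Combined Data columns may mean elapsed time since the parent first dose. SF-36, EQ-5D and visual function are reported as change from Previous Study Baseline, so sharing that origin is coherent: a value at combined Week 122 is 122 weeks after baseline. SAP 6.3.8 is also hedged as a general rule and lists no Combined Data target days, so a programmer could re-anchor.

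Part of this stands: elapsed time would be a defensible convention if stated. But the same section ties windows to protocol visits, and those are numbered from extension Day 1. Its only named exception is MRI. Even on elapsed time, columns after combined Week 96 in the placebo and glatiramer groups would mix values from before and after the first study dose of BG00012.

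Four stronger readings are tempting but not supported:
- *The by-visit tables exist to show the change at the switch to BG00012, and that contrast is spoiled.* No section says so. SAP 6.4.6 plans descriptive summaries from the parent baseline.
- *SF-36 and EQ-5D are broadly mislabelled.* Only about the last 2 of 26 permitted weeks of gap affect them.
- *Lymphocyte results are affected.* Use of Combined Data is optional there. For placebo and glatiramer subjects, SAP 6.3.1 makes the last value before extension dosing the BG00012 Treatment Baseline. If Combined Data were used, though, the same repeated value could serve as both baseline and a post-baseline visit.
- *A pre-dose value will appear as follow-up.* Repeating the baseline was allowed, not required.

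**Conclusion.** The point holds for subjects with a sufficient gap, in windowed by-visit summaries on Combined Data. As written, SAP 6.3.8 moves visual function visits at gaps of 6 and 12 weeks, SF-36 and EQ-5D at about 24 to 26 weeks, and 12-weekly lymphocytes at 6 weeks if Combined Data is used. A pre-dose value is mislabelled only if the baseline was also repeated.

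It does not touch subjects without a gap, primary safety analyses (extension data only), overall annualized relapse rate, Kaplan-Meier estimates or MRI by nominal visit. MRI is not wholly exempt, because premature-withdrawal scans are windowed and their anchor is not stated. The affected tables are descriptive and secondary, so no test or error rate changes.

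The documents give neither the number of subjects with a gap nor its length, so the effect on any group summary cannot be computed. The thresholds assume on-schedule visits; the allowed ±5 or ±7 days would shift them by up to about a week. The issue is modest, but worth correcting because the stated rule itself produces it and the remedy is small.

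**What to change.** Add to SAP 6.3.8:

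- In Combined Data, parent-study evaluations are windowed from the first parent-study dose and 109MS303 evaluations from the first 109MS303 dose, with extension columns labelled as 109MS303 weeks.
- No value on or before the first 109MS303 dose may fill a 109MS303 post-baseline window.
- The same anchor applies to windowed MRI premature-withdrawal scans from 109MS303, and the Day 169 bound is stated as counted from 109MS303 Day 1 if that is what was meant.

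It would also help to report how many subjects had a gap, and its distribution, so readers can judge how far extension weeks and elapsed time differ.

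The cost is a few sentences and a change of anchor date in the windowing program, with no new data. The one downside is that, for subjects with a gap, an extension column no longer equals a fixed time from Previous Study Baseline. A table footnote covers that.

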### 7.2.2. Treatment Period

Subjects will report to the study site every 4 weeks for the first 24 weeks (Visit 1 through Visit 6) and every 12 weeks thereafter.

Premature Study Treatment Withdrawal Visits and Unscheduled Relapse Assessment Visits will be performed as necessary. All efforts should be made to keep the subjects' visit schedule relative to their Baseline Visit (Day 1). Unscheduled Relapse Assessment Visits should not modify or replace their regular visit schedule.

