6.4.4 Analysis of Progression

Definition of Progression

In Study 109MS303, sustained disability progression will be assessed from the EDSS scores performed as per the protocol defined schedule of assessments at regular visits relative to the baseline EDSS score in the extension study, and well as from the baseline scores in previous study. Sustained disability progression is defined as at least a 1.0 point increase on the EDSS from a baseline EDSS ≥1.0 that is sustained for at least 24 weeks or a 1.5 point increase on the EDSS progression is defined as sustained (or confirmed) when this minimum EDSS change is present on the next study visit occurring after 154 days or longer from the initial observation. The 154 day interval is based on the visit windows allowed in the protocol around the target visit day

The date of the initial visit at which the minimum increase in the EDSS is met will be the date of onset of the progression (tentative progression).

Progression will not be confirmed at a visit where a relapse is also occurring. A subject is considered to be having a relapse for at least 29 days after the start date of an objective relapse. If a subject meets the defined EDSS criteria of sustained progression and is also having a relapse, the subject will be required to meet the defined minimum EDSS criteria at the subsequent visit.

Disability progression can be confirmed at the early (premature) study withdrawal visit, according to the rules above, as long as the early withdrawal visit is not also a relapse assessment visit.

Death due to MS will be counted as progression. If the subject was in the midst of a tentative progression at the time of death (e.g. the EDSS evaluation prior to death is a tentative progression), the progression date will be the date of the start of the progression. If the subject had a confirmed EDSS progression prior to death, the progression date is the start date of the tentative progression. Otherwise, the progression date will be the date of death.

In Studies 109MS301 and 109MS302, the same definition of sustained disability progression will be used as in Study 109MS303 (i.e., requiring a 24 week confirmation).

Sustained disability progression will be summarized using the following analysis populations, treatment groupings, and datasets:

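### The visit-window rule in SAP 6.3.8 lets SF-36, EQ-5D and visual function scores from relapse visits fill missed scheduled assessments and, rarely, displace attended ones

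*SAP*

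**What the plan says.** SAP 6.3.8 bases the analysis visit on the day of evaluation counted from first dose in the dataset, "rather than the nominal visit recorded in the clinical database". Its scope is broad but qualified: "In general, for data that are summarized by visit, visits for analysis will be assigned by using a windowing scheme as described below". The windows are contiguous: "windows will end at the midpoint between scheduled visit timepoints, with the midpoint in the latter visit window". Selection within a window is by distance, "If more than one observation occurs within the same window, data closest to the target day for the scheduled visit will be used for analysis", with a tie rule: "If more than one observation is the same distance from the target day, the last observation will be used for analysis". The one stated exception is imaging: apart from premature-withdrawal scans, "MRI analyses will not utilize visit windowing and will present results by nominal visit designations".

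Protocol 4.6 and 14.3.6 (repeated in SAP 3.6) schedule SF-36, EQ-5D and the visual function test at the Unscheduled Relapse Assessment Visit, which takes place within 5 days of a suspected relapse. SAP 6.4.6 and the table in 6.4.2.1 summarize these endpoints descriptively by treatment group and visit. The only data that 6.4.6 excludes are those after first use of an alternative MS medication.

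Protocol 7.2.2 tells sites that "Unscheduled Relapse Assessment Visits should not modify or replace their regular visit schedule". For disability progression, SAP 6.4.4 limits the data to "EDSS scores performed as per the protocol defined schedule of assessments at regular visits".

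**The concern.** The stated reason for windowing is that subjects do not keep exactly to the visit calendar. That justifies re-slotting a scheduled assessment that was early or late. It does not justify treating an assessment triggered by a suspected relapse as if it were the scheduled one.

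The rule cannot tell the two apart. A subject who misses the annual SF-36 and has no relapse visit contributes nothing. A subject who misses it and has a relapse visit in the window contributes a score taken during the suspected event. Gaps are therefore filled selectively, according to outcome. The by-visit mean becomes a mixture, probably shifted towards worse scores, and the mixing proportion rises with the relapse rate. Quality of life and visual function are named secondary objectives, so their tables should have one clear meaning.

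**Working it through.** The plan states no figure to reproduce, so the check applies the 6.3.8 rule to the extension schedule.

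Inputs from the documents:
- SF-36 and EQ-5D at Weeks 48, 96, and so on to 384. Visual function at Weeks 24 and 48, every 12 weeks to Week 144, then every 24 weeks (Protocol 4.1 to 4.3).
- Visit tolerance ±7 days from Week 36.
- Relapse rates of 0.44 and 0.65 per year from the Phase 2 study (Protocol 5.2), used only as illustration.

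Assumptions:
- Lower relapse rates of 0.1 and 0.2 per year; relapses follow a Poisson process, with one relapse visit per relapse.
- Target day = 7 × week + 1, counted from extension first dose.
- Windows follow each endpoint's own schedule.
- For step 4, r = 0.15 to 0.30 relapses per 48 weeks and m = 10% to 20% of annual assessments missed.

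1. **Windows.** The SF-36/EQ-5D targets for Weeks 48, 96 and 144 are Days 337, 673 and 1009. The midpoints are (337 + 673)/2 = 505 and (673 + 1009)/2 = 841. The Week 96 window is therefore Days 505-840, or 336 days, and later closed windows are the same length. The Week 48 window is Days 2-504. Visual function windows are 84 days at Weeks 60-132 and 168 days at Weeks 168-360.

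2. **Scheduled assessment missed.** Any relapse-visit score in the window becomes the visit value, up to about 168 days from target for SF-36/EQ-5D. The chance that the window holds at least one is P = 1 − exp(−rate × days/365.25):
   - 336 days: 8.8% (rate 0.1), 16.8% (0.2), 33.3% (0.44), 45.0% (0.65).
   - 168 days: 4.5% to 25.8% over the same range.
   - 84 days: 2.3% to 13.9%.

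3. **Scheduled assessment attended within ±7 days.** If it falls d days from target, a relapse visit is selected on 2|d| days when d is negative (it wins the later tie), 2d − 1 days when d is positive, and none when d = 0. Over d = −7 to +7 the mean is 7.0 days and the maximum 14. The average chance per window is 1 − exp(−rate × 7/365.25), which is 0.19% at 0.1 and 1.24% at 0.65. The largest value, 14 days at rate 0.65, is 2.5%. For example, with the scheduled visit 5 days late and a relapse visit 2 days before target, the relapse score is used.

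4. **Share of analysed annual scores.** With q = 7/336, share = [m(1 − e^−r) + (1 − m)rq] / [(1 − m) + m(1 − e^−r)].
   - r = 0.15, m = 0.1: (0.0139 + 0.0028)/(0.9 + 0.0139) = 0.0167/0.914 = 1.8%.
   - r = 0.30, m = 0.2: (0.0518 + 0.0050)/(0.8 + 0.0518) = 0.0568/0.852 = 6.7%.
   - The missed-visit term is 0.0139/0.0167 = 83% of the numerator in the first case and 0.0518/0.0568 = 91% in the second.

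5. **Other window basis.** The SAP does not say whether windows follow each endpoint's schedule or all protocol visits. With all visits, windows from Week 60 are 84 days. A relapse visit then fills an annual slot on only 84/336, or a quarter, of the days in step 1. On the other three quarters it creates an SF-36 value at a week where none was scheduled.

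6. **Combined Data.** These endpoints are analysed on Combined Data, so days run from first dose in the parent study. Extension baseline may be up to 6 months after parent Week 96, and the parent quality-of-life schedule is not in the documents. The bounds in step 1 are therefore illustrative.

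Under the proposed exclusion, the number of days on which a relapse-visit score can be selected is zero in every window.

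**The case against.** The strongest reply is that nothing here contradicts an analysis instruction. A reader might infer that the SAP breaches a protocol prohibition. It does not: Protocol 7.2.2 says should, not must, and it addresses sites about visit timing. The SAP departs from the intent of that sentence and no more. The windowing rule is also qualified in general terms, so a programmer could leave relapse visits out. Both points stand. But no text tells the programmer to do so, and two programmers could produce different tables.

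The size is weakly supported, and this stands too. The value of m must refer to subjects still followed who miss an annual assessment yet attend a relapse visit. Subjects who have left the study have no further relapse visits, their withdrawal visit itself collects SF-36 and EQ-5D, and data after alternative therapy are dropped. For attended visits the effect is close to negligible.

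The comparisons with other endpoints are limited. The relapse-visit task list has no MRI, so keeping nominal visits for MRI is no precedent. The EDSS restriction defines a sustained event, which is a different purpose from a descriptive mean. It shows only that the distinction between regular and relapse visits was available to the authors.

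Finally, excluding a relapse-visit score when it is the only one removes a relapser from that mean and could shift it upwards. That is a real cost, but the SAP's stated approach is observed data without imputation, and a missed scheduled assessment is better shown as missing.

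**Conclusion.** The gap is real and minor. SAP 6.3.8 as written permits relapse-visit SF-36, EQ-5D and visual function scores to enter by-visit summaries, mainly by filling missed assessments. The 2-7% share for annual quality-of-life scores depends on the assumed r and m and on endpoint-specific windows, none of which the documents supply. Suspected relapses that are not confirmed also trigger the visit, so visits may outnumber confirmed relapses.

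Three stronger readings are tempting but unsupported:
- **A point shift in the means.** An assumed drop of 5-10 points times 1.8-6.7% gives 0.09-0.67 points. One drop cannot serve the EQ-5D index, a 0-100 scale and a 60-letter chart, and the documents give no drop for any of them.
- **A biased group comparison.** The direction is plausible if relapse rates differ, but any such bias would be only the difference between two within-group shifts, and nothing in the documents allows it to be calculated.
- **The same fault in vital signs and laboratory summaries.** No relapse-related distortion is shown there, and those data serve the primary safety objective.

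The affected endpoints are secondary and descriptive. The primary objective, the annualized relapse rate and EDSS progression are untouched.

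**What to change.** Add one sentence to SAP 6.3.8 or 6.4.6: SF-36, EQ-5D and visual function scores whose nominal visit is the Unscheduled Relapse Assessment Visit are not eligible for by-visit windows and are listed separately. At minimum, state that a scheduled assessment in the window always takes precedence. That lesser rule stops displacement but leaves the main route, the missed assessment, open. In the same edit, say whether windows follow each endpoint's own schedule or all protocol visits.

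Leave vital-sign and laboratory windowing unchanged. The cost is a filter on the nominal visit, a field that 6.3.8 shows is already in the database, plus one listing. No new data are needed. Some subjects with a missed scheduled assessment will have no value at that visit, so show the number contributing at each visit.
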